Appendix 11: Clinical Outcome Assessment Instruments

SCID-5-CT Modified For Roche BN43546 Nov 2021

Page 21

Have you ever thought that you were especially important in some way, or that you had special powers or knowledge? (Tell me about that.)
 
Did you ever believe that you had a special or close relationship with a celebrity or someone else famous?
	
Grandiose delusion, i.e., content involves exaggerated power, knowledge or importance, or a special relationship to a deity or famous person
 
DESCRIBE:
	
– +

Have you ever been convinced that something was very wrong with your physical health even though your doctor said nothing was wrong . . . like you had cancer or some other disease? (Tell me about that.)
 
Have you ever felt that something strange was happening to parts of your body?'
	
Somatic delusion, i.e., content involves change or disturbance in body appearance or functioning.
 
DESCRIBE:
	
– +

Have you ever felt that you had committed a crime or done something terrible for which you should be punished? (Tell me about that.)
 
Have you ever felt that something you did, or should have done but did not do, caused serious harm to your parents, children, other family members, or friends? (Tell me about that.)
 
What about feeling responsible for a disaster such as a fire, flood, or earthquake? (Tell me about that.)
	
Delusion of guilt. i.e., a belief that a minor error in the past will lead to disaster, or that he or she has committed a horrible crime and should be punished severely, or that he or she is responsible for a disaster (e.g., an earthquake or fire) with which there can be no possible connection
 
DESCRIBE:
	
– +

Have you ever been convinced that your spouse or partner was being unfaithful to you?
 
IF YES: How did you know he/she was being unfaithful? (What clued you into this?)
	
Jealous delusion, i.e., that one's sexual partner is unfaithful
 
DESCRIBE:
	
– +

Did you ever have a "secret admirer" who, when you tried to contact them, denied that they were in love with you? (Tell me about that.)
 
Were you ever romantically involved with someone famous? (Tell me about that.)
	
Erotomanic delusion, i.e., that another person, usually of higher status, is in love with the individual.
 
DESCRIBE
	
– +

Appendix 11: Clinical Outcome Assessment Instruments

Are you a religious or spiritual person?
 
→ IF YES: Have you ever had any religious or spiritual experiences that the other people in your religious or spiritual community have not experienced?
 
→ IF YES: Tell me about your experiences. (What did they think about these experiences of yours?)
 
→ IF NO: Have you ever felt that God, the devil, or some other spiritual being or higher power has communicated directly with you? (Tell me about that. Do others in your religious or spiritual community also have such experiences?)
 
→ IF NO: Have you ever felt that God, or the devil or some other spiritual being or higher power has communicated directly with you? (Tell me about that. Do others in your religious or spiritual community also have such experiences?)
	
Religious delusion, i.e., a delusion with a religious or spiritual content.
 
DESCRIBE:
	
– +

Did you ever feel that someone or something outside yourself was controlling your thoughts or actions against your will? (Tell me about that.)
	
Delusion of being controlled, i.e., feelings, impulses, thoughts, or actions are experienced as being under the control of some external force rather than under one's own control.
 
DESCRIBE:
	
– +

Did you ever feel that certain thoughts that were not your own were put into your head? (Tell me about that.)
	
Thought insertion, i.e., that certain thoughts are not one's own, but rather are inserted into one's mind.
 
DESCRIBE:
	
– +

What about thoughts being taken out of your head? (Tell me about that.)
	
Thought withdrawal, i.e., that one's thoughts have been "removed" by some outside force.
 
DESCRIBE:
	
– +

Did you ever feel as if your thoughts were being broadcast out loud so that other people could actually hear what you were thinking? (Tell me about that.)
	
Thought broadcasting, i.e., the delusion that one's thoughts are being broadcast out loud so that others can perceive them.
	
– +

Did you ever believe that someone could read your mind? (Tell me about that.)
	
Other delusions (e.g., that others can read the person's mind, a delusion that one has died several years ago)
 
DESCRIBE:
	
– +

Appendix 11: Clinical Outcome Assessment Instruments

[figure not shown]
	
HALLUCINATIONS
 
A perception-like experience with the clarity and impact of a true perception, but without the external stimulation of the relevant sensory organ. The person may or may not have insight into the nonveridical nature of the hallucination (i.e., one hallucinating person may recognize the false sensory experience, whereas another may be convinced that the experience is grounded in reality).
 
Note: Code “-” for hallucinations that are so transient as to be without diagnostic significance. Code “-” for hypnagogic or hypnopompic hallucinations occurring when falling asleep or upon awakening
	

Did you ever hear things that other people couldn’t, such as noises, or the voices of people whispering or talking? (Were you awake at the time?)
 
IF YES: What did you hear? How often did you hear it?
	
Auditory hallucinations (i.e., involving the perception of sound, most commonly of voice) when fully awake, heard either inside or outside of one’s head.
 
DESCRIBE:
	
– +

Did you have visions or see things that other people couldn’t see? (Tell me about that. Were you awake at the time?)
	
Visual hallucinations (i.e., a hallucination involving sight, which may consist of formed images, such as of people or of unformed images, such as flashes of light.)
 
Note: Distinguish from an illusion, i.e., a misperception of a real external stimulus
 
DESCRIBE:
	
– +

What about strange sensations on your skin, like feeling like something is creeping or crawling on or under your skin? How about the feeling of being touched or stroked? (Tell me about that.)
	
Tactile hallucinations, i.e., a hallucination involving the perception of being touched or of something being under one’s skin.
 
DESCRIBE
	
– +

What about having unusual sensations inside a part of your body, like a feeling of electricity? (Tell me about that.)
	
Somatic hallucinations, i.e., a hallucination involving the perception of physical experience localized within the body (e.g., a feeling of electricity).
 
DESCRIBE:
	
– +

Appendix 11: Clinical Outcome Assessment Instruments

SCID-5-CT Modified For Roche BN43546 Nov 2021

Page 24

How about eating or drinking something that you thought tasted bad or strange even though everyone else who tasted it thought it was fine? (Tell me about that.)
	
Gustatory hallucinations, i.e., a hallucination involving the perception of taste (usually unpleasant)
 
DESCRIBE
	

What about smelling unpleasant things that other people couldn't smell, like decaying food or dead bodies? (Tell me about that.)
	
Olfactory hallucinations, i.e., a hallucination involving the perception of odor
 
DESCRIBE:
	
	
ANY PSYCHOTIC ITEM CODED "+"
	
NO YES

Appendix 11: Clinical Outcome Assessment Instruments

SUBSTANCE USE DISORDERS		
ALCOHOL USE DISORDER PAST SIX MONTHS		

What are your drinking habits like? (How much do you drink?)
 
Have you drunk alcohol at least six times in the past 12 months, that is, since (12 MONTHS AGO)?
		
IF DID NOT DRINK AT LEAST SIX TIMES IN PAST 12 MONTHS, SKIP TO *NON-ALCOHOL SUBSTANCE USE,* PAGE 29.		
	ALCOHOL USE DISORDER CRITERIA	
I'd now like to ask you some more questions about your drinking habits since (12 MONTHS AGO)....	A. A problematic pattern of alcohol use, leading to clinically significant impairment or distress, as manifested by at least two of the following occurring within a 12-month period:	

During the past 12 months...
 
...have you found that once you started drinking you ended up drinking much more than you intended to? For example, you planned to have only one or two drinks but you ended up having many more. (Tell me about that. How often did this happen?)
 
IF NO: What about drinking for a much longer period of time than you were intending to?
	1. Alcohol is often taken in larger amounts OR over a longer period than was intended.	- +

...have you wanted to stop, cut down, or control your drinking?
 
▶ IF YES: How long did this desire to stop, cut down, or control your drinking last?
 
▶ IF NO: During the past two months, did you ever try to cut down, stop, or control your drinking? How successful were you? (Did you make more than one attempt to stop, cut down, or control your drinking?)
	2. There is a persistent desire OR unsuccessful efforts to cut down or control alcohol use.	- +
...have you spent a lot of time drinking, being drunk, or hung over? (How much time?)...	3. A great deal of time is spent in activities necessary to obtain alcohol, use alcohol, or recover from its effects.	- +

Appendix 11: Clinical Outcome Assessment Instruments

SCID-5-CT Modified For Roche BN43546 Nov 2021

Page 26

During the past 12 months, since (12 MONTHS AGO)...
 
...have you had a strong desire or urge to drink in between those times when you were drinking? (Has there been a time when you had such strong urges to have a drink that you had trouble thinking about anything else?)
 
IF NO: How about having a strong desire or urge to drink when you were around bars or around people with whom you go drinking?
	
4. Craving, or a strong desire or urge to use alcohol.
	
– +

...have you missed work or school or often arrived late because you were intoxicated, high, or very hung over?
 
IF NO: How about doing a bad job at work or school, or failing courses or getting kicked out of school because of your drinking?
 
IF NO: How about getting into trouble at work or school because of your use of alcohol?
 
IF NO: How about not taking care of things at home because of your drinking, like making sure there is food and clean clothes for your family and making sure your children go to school and get medical care? How about not paying your bills?
 
IF YES TO ANY: How often?
	
5. Recurrent alcohol use resulting in a failure to fulfill major role obligations at work, school, or home (e.g., repeated absences or poor work performance related to alcohol use; alcohol-related absences, suspensions, or expulsions from school; neglect of children or household).
	
– +

...has your drinking caused problems with other people, such as family members, friends, or people at work? (Have you found yourself regularly getting into arguments about what happens when you drink too much? Have you gotten into physical fights when you were drunk?)
 
IF YES: Did you keep on drinking anyway? (Over what period of time)?
	
6. Continued alcohol use despite having persistent or recurrent social or interpersonal problems caused or exacerbated by the effects of alcohol (e.g., arguments with spouse about consequences of intoxication, physical fights).
	
– +

...have you had to give up or reduce the time you spent at work or school, with family or friends, or on things you like to do (like sports, cooking, other hobbies) because you were drinking or hungover?
	
7. Important social, occupational, or recreational activities given up or reduced because of alcohol use.
	
– +

Appendix 11: Clinical Outcome Assessment Instruments

SCID-5-CT Modified For Roche BN43546 Nov 2021

Page 27

During the past 12 months, since (12 MONTHS AGO)...
 
...have you ever had a few drinks right before doing something that requires coordination and concentration like driving, boating, climbing on a ladder, or operating heavy machinery?
 
IF YES: Would you say that the amount you had to drink affected your coordination or concentration so that it was more likely that you or someone else could have been hurt?
 
IF YES AND UNKNOWN: How many times? (When?)
	
8. Recurrent alcohol use in situations in which it is physically hazardous (e.g., driving an automobile or operating a machine when impaired by alcohol use).
	
— +

...has your drinking caused you any problems like making you very depressed or anxious? How about putting you in a "mental fog," making it difficult for you to sleep, or making it so you couldn't recall what happened while you were drinking?
 
Has your drinking caused significant physical problems or make a physical problem worse, like stomach ulcers, liver disease, or pancreatitis?
 
IF YES TO EITHER OF ABOVE: Did you keep on drinking anyway?
	
9. Alcohol use is continued despite knowledge of having a persistent or recurrent physical or psychological problem that is likely to have been caused or exacerbated by alcohol (e.g., continued drinking despite recognition that an ulcer was made worse by alcohol consumption).
	
— +

...have you ever found that you needed to drink much more in order to get the feeling you wanted than you did when you first started drinking?
 
IF YES: How much more?
 
IF NO: What about finding that when you drank the same amount, it had much less effect than before? (How much less?)
	
10. Tolerance, as defined by either of the following:
 
a. A need for markedly increased amounts of alcohol to achieve intoxication or desired effect.
 
b. Markedly diminished effect with continued use of the same amount of alcohol
	
— +

Appendix 11: Clinical Outcome Assessment Instruments

During the past six months, since (SIX MONTHS AGO)...
 
...have you ever had any withdrawal symptoms, in other words felt sick when you cut down or stopped drinking?
 
→ IF YES: What symptoms did you have? (Sweating or a racing heart? Your hand(s) shaking? Trouble sleeping? Feeling nauseated or vomiting? Feeling agitated? Feeling anxious? How about having a seizure or seeing, feeling, or hearing things that weren't really there?)
 
→ IF NO: Have you ever started the day with a drink, or did you often drink or take some other drug or medication to keep yourself from getting the shakes or becoming sick?
	
11. Withdrawal, as manifested by either of the following:
 
a. At least TWO of the following developing within several hours to a few days after the cessation of (or reduction in) alcohol use:
 
 -- autonomic hyperactivity (e.g., sweating or pulse rate greater than 100 bpm) -- increased hand tremor -- insomnia -- nausea or vomiting -- psychomotor agitation -- anxiety -- generalized tonic-clonic seizures -- transient visual, tactile, or auditory hallucinations or illusions 
b. Alcohol (or a closely related substance such as a benzodiazepine) is taken to relieve or avoid withdrawal symptoms,
	
- +

IF UNCLEAR: When did (SXS RATED "+" ABOVE) occur? (Did they all happen within the past 12 months?)
	
AT LEAST TWO ALCOHOL USE ITEMS CODED "+" AND ITEMS OCCURRED DURING THE LAST 12 MONTHS
	
NO YES
 
Continue on next page

COUNT THE NUMBER OF SYMPTOMS RATED "+." IF TWO OR MORE, EXCLUDE FROM STUDY
		

Appendix 11: Clinical Outcome Assessment Instruments

NON-ALCOHOL SUBSTANCE USE DISORDER	
Now I'd like to ask you about your use of drugs or medicines over the past 12 months, since (12 MONTHS AGO).	
Drug Classes to Be Inquired About:	Indicate Use Pattern Based on Questions at Bottom of the Page
Sedatives-hypnotics-anxiolytics: In the past 12 months, Have you taken any pills to calm you down, help you relax, or help you sleep? (Drugs like Vallium, Xanax, Ativan, Klonopin, Ambien, Sonata or Lunesta?)	
Cannabis: In the past 12 months, Have you used marijuana ("pot", "grass", "weed"), hashish ("hash"), THC, K2, or "spice"?	
Stimulants: In the past 12 months, Have you used any stimulants or "uppers" to give you more energy, keep you alert, lose weight, or help you focus? (Drugs like speed, methamphetamine, crystal meth, "crank," Ritalin or methylphenidate, Dexedrine, Adderall or amphetamine or prescription diet pills?) How about cocaine or "crack"?	
Opioids: In the past 12 months, Have you ever used heroin or methadone? How about prescription pain killers? (Drugs like morphine, codeine, Percocet, Percodan, Oxycontin, Tylox, or oxycodone, Vicodin, Lortab, Lorcet or hydrocodone, suboxone or buprenorphine?)	
Phencyclidine and Related Substances: In the past 12 months, Have you ever used PCP ("angel dust," "peace pill") or ketamine ("Special K," "Vitamin K	
Other Hallucinogens: In the past 12 months, have you used any drugs to "trip" or heighten your senses? (Drugs like LSD, "acid", peyote, mescaline, "mushrooms," psilocybin, Ecstasy (MDMA, "molly"), bath salts, DMT, or other hallucinogens?)	
Inhalants: In the past 12 months, have you ever used glue, paint, or correction fluid, gasoline, or other inhalants to get high?	
Other: What about other drugs, like anabolic steroids, nitrous oxide (laughing gas, "whippets"), nitrites (amyl nitrite, butyl nitrite, "poppers," "snappers"), diet pills (phentermine), or over-the-counter medicine for allergies, colds, cough, or sleep?	
IF NO ILLEGAL OR RECREATIONAL DRUGS USED AT LEAST SIX TIMES WITHIN THE PAST 12 MONTHS AND NEVER ABUSED ANY OVER-THE-COUNTER OR PRESCRIBED MEDICATIONS (E.G., TAKING MORE THAN PRESCRIBED OR RECOMMENDED, OR DOCTOR-SHOPPING TO GET PRESCRIPTIONS) IN PAST 12 MONTHS, END OF SCID.	
IF ACKNOWLEDGES USE OF A DRUG FROM ANY CLASS BELOW, FOLLOW UP WITH THE FOLLOWING QUESTIONS:	
During the past 12 months, when were you taking (SUBSTANCE) the most? How long did that period last? During that time, how often were you taking it? How much were you using?	
During the past 12 months, have you had a time when your use of (SUBSTANCE) caused problems for you? During the past 12 months, has anyone objected to your use of (SUBSTANCE)?	
IF ILLICIT OR RECREATIONAL DRUG: Have you used (SUBSTANCE) at least six times during the past 12 months?	
IF PRESCRIBED/OTC MEDICATION AND UNKNOWN: Over the past 12 months, did you get hooked or become dependent on (PRESCRIBED DRUG)? Did you ever take more of it than was prescribed or run out of your prescription early? (Did you ever have to go to more than one doctor to make sure you didn't run out?)	

Appendix 11: Clinical Outcome Assessment Instruments

NON-ALCOHOL SUBSTANCE DEPENDENCE	SUBSTANCE USE DISORDER CRITERIA	

Which drugs or medications caused you the most problems over the past 12 months, since (12 MONTHS AGO)? Which ones did you use the most? Which were your "drugs of choice?"
		

I'd now like to ask you some more questions about your use of (SUBSTANCE USED MOST HEAVILY OR CAUSED MOST PROBLEMS) in the past 12 months, since (12 MONTHS AGO).
	
A. A problematic pattern of substance use leading to clinically significant impairment or distress, as manifested by at least two of the following occurring within a [6]-month period:
	

During the past 12 months...
 
...have you found that once you started using (DRUG) you ended up using much more than you intended to? For example, you planned to have (SMALL AMOUNT OF DRUG) but you ended up having much more. (Tell me about that. How often did that happen?)
 
IF NO: What about using (DRUG) for a much longer period of time than you were intending to?
	
1. The substance is often taken in larger amounts OR over a longer period than was intended.
	
– +

...have you wanted to stop or cut down using (DRUG), or control your use of (DRUG)?
 
→ IF YES: How long did this desire to stop, cut down, or control your use of (DRUG) last?
 
→ IF NO: During the past year, did you ever try to cut down, stop, or control your use of (DRUG)? How successful were you? (Did you make more than one attempt to stop, cut down, or control your use of (DRUG)?)
	
2. There is a persistent desire OR unsuccessful efforts to cut down or control substance use.
	
– +

...have you spent a lot of time getting (DRUG) or using (DRUG) or has it taken a lot of time for you to get over the effects of (DRUG)? (How much time?)
	
3. A great deal of time is spent in activities necessary to obtain the substance, use the substance, or recover from its effects.
	
– +

...have you had a strong desire or urge to use (DRUG) in between those times when you were using (DRUG)? (Has there been a time when you had such strong urges to use (DRUG) that you had trouble thinking about anything else?)
 
IF NO: How about having a strong desire or urge to use (DRUG) when you were around people with whom you used (DRUG)?
	
4. Craving, or a strong desire or urge to use the substance.
	
– +

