5.2 EXCLUSION CRITERIA

Potential participants are excluded from the study if any of the following criteria apply:

- Ongoing exposure to traumatic events within 3 months of screening
- Pregnant or breastfeeding, or intending to become pregnant during the study or within 14 days after the final dose of study drug
- Concurrent use of any of the prohibited medications and food products listed in Section 6.8.3
- Any clinically significant psychiatric and/or neurological conditions, which may interfere with the assessment of safety or efficacy endpoints. This includes:
 - Any contraindications to EEG (e.g., requiring high concentration oxygen)
 - Significant risk for suicidal behavior, as assessed by the investigator, or a score of 4 or 5 on the C-SSRS in the past 6 months or category 6 or greater on the C-SSRS in the past 12 months (for C-SSRS categories and score see Section 8.2.7)
 - Diagnosis of schizophrenia, bipolar disorder, other psychotic disorder, or cognitive disorder, as defined by DSM-5
 - Epilepsy or seizure disorder considered not well controlled within the past 6 months or changes in anticonvulsive therapy within the last 6 months
 - Clinical diagnosis of peripheral neuropathy or signs and symptoms indicative of peripheral neuropathy
 - Substance use disorders (including alcohol or substance abuse or dependence disorder) during the last 12 months, as defined using the DSM-5 criteria
 - Diagnosis of traumatic brain injury

- Any cardiovascular disorders such as:
 - Uncontrolled hypertension (e.g., blood pressure repeatedly >160 mmHg systolic or >95 mmHg diastolic)
 - Within the last 2 years, unstable or clinically significant cardiovascular disease (e.g., myocardial infarction, angina pectoris, or New York Heart Association Class II or higher cardiac failure)
 - Confirmed (e.g., on two consecutive measurements *taken approximately 30 minutes apart during screening; the second measurement is only taken if it is necessary to confirm initial ECG abnormality*) clinically significant abnormality on ECG at screening, including, but not limited to, a QT interval corrected through the use of Fridericia's formula (QTcF) of ≥ 450 ms *in male participants and ≥ 470 ms in female participants*, absence of dominating sinus rhythm, or second- or third-degree atrioventricular block
 - Confirmed elevation above upper limit of normal (ULN) of high-sensitivity cardiac troponin T (hs-cTnT)
 - Unexplained syncopal episode within the last 12 months

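### Part of the study-modified SCID-5 alcohol module looks back only six or two months, while Section 5.2 excludes substance use disorder over 12 months

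*Combined protocol and SAP*

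**What the plan says.** The protocol's exclusion (Section 5.2) is: "Substance use disorders (including alcohol or substance abuse or dependence disorder) during the last 12 months, as defined using the DSM-5 criteria". It does not name the instrument that establishes this.

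The SCID-5 in Appendix 11 is marked as modified for this study in November 2021. Its alcohol module is headed "ALCOHOL USE DISORDER PAST SIX MONTHS". Criterion A of that module nevertheless reads "as manifested by at least two of the following occurring within a 12-month period", and the closing count requires at least two positive items "AND ITEMS OCCURRED DURING THE LAST 12 MONTHS". Two or more positive items lead to an instruction to exclude.

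Two alcohol prompts use shorter periods. The withdrawal item opens with "During the past six months, since (SIX MONTHS AGO". The item on cutting down has a follow-up for those who deny wanting to stop, cut down or control their drinking: "During the past two months, did you ever try to cut down, stop, or control your drinking".

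In the non-alcohol module, criterion A reads "as manifested by at least two of the following occurring within a [6]-month period". The introduction, the drug-class questions and the dated item prompts there refer to the past 12 months or the past year.

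Section 8.1.1.6 says that the SCID-5 serves only to diagnose PTSD, at screening.

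**The concern.** An eligibility form should ask about the same period as the criterion it serves. Here the criterion and most of the form use 12 months, but a few prompts and one rule do not, and nothing in the documents explains the shorter periods. They look like remnants of a template.

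Section 5.2 lists substance use disorder among conditions that may interfere with the safety or efficacy endpoints. The documents name no other structured instrument for diagnosing it. The urine test in the schedule of activities detects the presence of substances, and the medical history records use of alcohol and drugs; neither is a count of DSM-5 criteria over a year. If the form's windows are too short, a person who meets the exclusion may not be flagged by the one structured check that carries an exclusion instruction.

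**Working it through.** No arithmetic in the plan bears on this, so the check sets the printed windows side by side and applies the two-item rule to example timings.

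| Place | Window | Part of the 12 months not covered |
|---|---|---|
| Section 5.2 exclusion | 12 months | none |
| Alcohol heading | 6 months | label only |
| Alcohol criterion A and closing count | 12 months | none |
| Alcohol items 1 to 10, main prompts | 12 months | none |
| Alcohol item 2, follow-up after a no | 2 months | 12 − 2 = 10 months |
| Alcohol item 11, withdrawal | 6 months | 12 − 6 = 6 months |
| Non-alcohol criterion A | [6] months, as a clustering rule | see example 3 |
| Non-alcohol item 2, follow-up after a no | past year | none |

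The last row matters: the drug version of the same follow-up question uses a year, so the two-month period in the alcohol version is not a deliberate feature of the item.

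**Example 1, alcohol withdrawal.** Tolerance and withdrawal both occurred about 9 months ago. Tolerance is asked over 12 months and is positive. Withdrawal is asked over 6 months, and 9 > 6, so it is not positive. The count is 1, below 2, and the form does not exclude, although two criteria fell within 12 months.

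**Example 2, alcohol cut-down.** One other item is positive, and there were failed attempts to cut down about 5 months ago, but the person reports no wish to stop or cut down. The follow-up covers 2 months, and 5 > 2, so item 2 is negative. The count is again 1.

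**Example 3, drugs.** One criterion was met about 1 month ago and another about 10 months ago. They are 10 − 1 = 9 months apart: inside 12 months, but not inside any 6-month period. Criterion A as printed is not met, yet both items would be rated positive on 12-month prompts. Which prevails depends on that module's closing count, which is not legible in the copy examined. The result is therefore undetermined.

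**Contrast.** Anyone with two alcohol items that are both asked on 12-month prompts is still caught.

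The 12-month closing count does not rescue examples 1 and 2. It asks when the items already rated positive occurred; it does not reopen an item rated negative because its prompt covered a shorter period.

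**The case against.** The strongest reply is that Section 5.2 stands on its own. It sets 12 months under DSM-5 and does not mention the SCID-5. Section 8.1.1.6 confines the SCID-5 to PTSD. Screening also takes an alcohol and drug history, the SCID-5 overview asks about past treatment for drugs or alcohol, and a general investigator-judgement exclusion applies. This stands: not being flagged by the form is not the same as being enrolled.

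Second, a reader might infer that the whole drug module works on six months. The documents do not support that. Its dated prompts use a year, its withdrawal item carries no period of its own, and no visible prompt asks whether two items fell within six months of each other.

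Third, the alcohol heading is only a label, and the two-month question is reached only after a negative answer to a 12-month question. It misses only people who tried to cut down yet report no wish to. This also stands, and leaves the withdrawal prompt as the one clear gap. That prompt does contain the word ever, so a respondent might volunteer an older episode, but its opening words fix the period at six months.

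Appendix 11 warns that instruments may look different on the electronic device. That does not help here, because the same note excepts the SCID-5 from electronic completion.

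**Conclusion.** Wrong as written, and minor. The SCID-5 does not consistently screen for the period that Section 5.2 sets. The people not flagged are those near the two-item threshold whose deciding alcohol item is either withdrawal 7 to 12 months ago, or failed cut-down attempts more than two months ago without a reported wish to stop. This assumes that interviewers follow the form as printed. The bracketed six-month figure for drugs is a visible conflict whose practical effect is uncertain.

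A reader might go further and conclude that participants with active substance use disorder will enter the trial and distort the means of two arms of about 15. The documents do not support this. The alcohol examples turn on past events rather than current disorder, the independent exclusion and history may catch such people, and nothing gives the prevalence or timing needed to say how many are affected. No effect on the arm means is claimed. Nor is safety the sole stated reason for the exclusion.

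**What to change.** Bring the form into line with the 12-month period in Section 5.2:

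- change the period in the alcohol withdrawal prompt;
- change the period in the alcohol cut-down follow-up, as its drug counterpart already does;
- correct the alcohol heading;
- replace the bracketed figure in non-alcohol criterion A, and confirm that the module's closing count uses the same period;
- give the drug withdrawal item an explicit period.

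Then reconcile Section 8.1.1.6 with the form. Either say that the SCID-5 also supports the substance-use exclusion, or state which assessment does and remove the form's exclusion instruction.

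The cost is a few text edits to a form the sponsor has already modified, and one sentence in the protocol. The design, sample size and analysis do not change.
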